### **15.** Compensation, Insurance, and Indemnity

The financial agreement, insurance and indemnity between sponsor and investigators are provided in separate agreements.

### **16.** Publication Policy

The existence of this clinical study is confidential, and it should not be discussed with persons outside of the study. Additionally, the information in this document and regarding this Study contains trade secrets and commercially sensitive information that is confidential and may not be disclosed unless such disclosure is required by regional or national law or regulations. Subject to the foregoing, this information may be disclosed only to those persons involved in the study who have a need to know, but all such persons must be instructed not to further disseminate this information to others. These restrictions of disclosure will apply equally to all future information provided that is indicated as confidential.

The data generated by this clinical study are the property of the Sponsor. These data may be used by the Sponsor now and in the future for presentation or publication at Sponsor's discretion or for submission to governmental regulatory agencies. The Principal Investigator(s) may publish or present the Study results with prior consent of the Sponsor but will not disclose confidential information.

Prior to submission by a Principal Investigator for publication or presentation, the Sponsor will be provided with the opportunity to review the submission for confidential information and accuracy.

#### 17.2 Appendix II Regulatory Considerations

Sponsor, in cooperation with the Investigator, will make necessary efforts to ensure that this study is conducted in compliance with GCPs and all applicable regulatory requirements.

### **Pre-Study Documentation Requirements**

Prior to shipment of product, the following documents must be provided to Sponsor:

- Signed and dated Investigator Agreement
- A copy of the written IRB approval of the protocol
- A copy of the written IRB approval of the Informed Consent Form and HIPPA authorization document
- A copy of the curriculum vitae of the Principal Investigator and Co-Principal Investigator (if applicable)

### General Duties [21 CFR 812. 40]

No IDE application to FDA is required for this Study. The Sponsor and the Investigator are responsible for obtaining IRB approval prior to start of the study. Sponsor will be responsible for providing quality data that satisfies publication requirements and informing of serious unanticipated adverse events and deviations from the protocol.

#### Monitoring [21 CFR 812. 46]

Sponsor or its designee will conduct investigational site monitoring to ensure that all Investigators are in compliance with the protocol and the Investigators' agreements. The sponsor and/or designee will monitor the site to ensure that the completed Case Report Forms match the medical records, and resolve any differences. The sponsor will retain the right to remove either the Investigator or the investigational site from the study.

The sponsor will review significant new information, including unanticipated serious adverse events and ensure that such information is provided to the Investigators and to all reviewing IRB.

#### Supplemental Applications [21 CFR 812. 335 (A) and (B)]

As appropriate, the sponsor will submit changes in the Investigational Plan to the Investigators to obtain IRB re-approval. No FDA submissions are required.

### Maintaining Records [21 CFR 812. 140 (B)]

The sponsor will maintain copies of correspondence, data, shipment of devices, serious adverse device effects and other records related to the clinical Study. The sponsor will maintain records related to the signed Investigator Agreements.

### Submitting Reports [21 CFR 812. 150 (B)]

No FDA submissions are required for the Study.

### Site Record Retention Policy [21 CFR 812. 140 (D)]

The sponsor and clinical site will maintain all records pertaining to this study for a period of two

Printed copies are considered UNCONTROLLED documents after the date printed. Printed on September 17, 2024. CONFIDENTIAL, PROPRIETORY OF AURIS HEALTH, INC

PROTOCOL	Doc #:	104-010990-00
First-in-Human Study Protocol — Monarch Urology		С
(Protocol No.: 2021-URO-0001)	Page:	43 of 48

years following: the date on which the investigation is terminated or completed, or the date that the records are no longer required for purposes of supporting a pre-market approval application. Record retention dates will be provided to all concerned by the sponsor.

#### Informed Consent & Institutional Review Board/Ethic Committee [21 CFR Parts 50 & 56]

All subjects must provide written informed consent in accordance with the local clinical site's IRB. A copy of the consent form from each center must be forwarded to the Sponsor for review and approval prior to submitting it to the IRB. The site must provide the Sponsor with a copy of the clinical site's IRB approval letter and the informed consent. Yearly approvals for the continuation of the Study at each clinical site must also be forwarded to the Sponsor.

All Protected Health Information (PHI) to be collected in the study will be described in the informed consent form, and all study data will be managed in accordance with the Privacy Law (HIPAA).

	PROTOCOL	Doc #:	104-010990-00
	First-in-Human Study Protocol – Monarch Urology	Rev:	С
AURIS	(Protocol No.: 2021-URO-0001)	Page:	44 of 48

# **17.3** Appendix III

## **Clavien-Dindo Classification**

### For classification of adverse events

Adverse events will be graded using the Clavien-Dindo Classification system. First described in 2004, it is widely used throughout surgery for grading adverse events (i.e. complications), which occur as a result of surgical procedures.a

Clavien-Dindo consists of 7 grades (I, II, IIIa, IIIb, IVa, IVb and V). The introduction of the subclasses a and b allows a contraction of the classification into 5 grades (I, II, III, IV and V) depending on the size of the population observed or the of the focus of a study.

Complications that have the potential for long-lasting disability after patient's discharge (e.g.: paralysis of a voice cord after thyroid surgery) are highlighted in the present classification by a suffix ("d" for disability). This suffix indicates that a follow-up is required to comprehensively evaluate the outcome and related long-term quality of life.

Grades	Definition
Grade I	Any deviation from the normal postoperative course without the need for pharmacological treatment or surgical, endoscopic, and radiological interventions. Allowed therapeutic regimens are: drugs as antiemetics, antipyretics, analgesics, diuretics and electrolytes and physiotherapy. This grade also includes wound infections opened at the bedside.
Grade II	Requiring pharmacological treatment with drugs other than such allowed for grade I complications. Blood transfusions and total parenteral nutrition are also included.
Grade III	Requiring surgical, endoscopic, or radiological intervention
- IIIa	Intervention not under general anesthesia
- IIIb	Intervention under general anesthesia
Grade IV	Life-threatening complication (including CNS complications)* requiring IC/ICU- management
- IVa	single organ dysfunction (including dialysis)
- IVb	Multiorgan dysfunction
Grade V	Death of a patient

\*brain hemorrhage, ischemic stroke, subarrachnoidal bleeding, but excluding transient ischemic attacks (TIA); IC: Intermediate care; ICU: Intensive care unit.

a Dindo D, Demartines N, Clavien PA. Classification of surgical complications: a new proposal with evaluation in a cohort of 6336 patients and results of a survey. Ann Surg. 2004;240:205–213.

Printed copies are considered UNCONTROLLED documents after the date printed. Printed on September 17, 2024. CONFIDENTIAL, PROPRIETORY OF AURIS HEALTH, INC

PROTOCOL	Doc #:	104-010990-00
First-in-Human Study Protocol – Monarch Urology		С
(Protocol No.: 2021-URO-0001)	Page:	45 of 48

## 17.5 Appendix IV

Refer to Figure 2 for MONARCHTM Platform, Urology capital equipment setup. Table 2 provides an overview description of MONARCHTM Platform, Urology's capital components and MONARCHTM Platform, Urology instruments and accessories kits that will be provided by the manufacturer, Auris Health, Inc.

### Figure 2: MONARCHTM Platform, Urology Capital Equipment Setup

An overview of major capital components and instruments and accessories kits of the MONARCHTM Platform, Urology provided by Auris Health, Inc. are described in **Table 2**.

PROTOCOL	Doc #:	104-010990-00
First-in-Human Study Protocol – Monarch Urology	Rev:	С
(Protocol No.: 2021-URO-0001)		46 of 48

Capital Components	
MONARCHTM Tower Main Tower that connects with the major components (Cart, Fluid Management Controller, Ureteroscope, Compact Field Generator, Percutaneous Needle) of the platform to enable use of the Urology indication. The Tower has a user interface screen and houses the necessary hardware and software to operate the system.	
MONARCH TM Cart	Mobile Cart that is comprised of three robotic arms and a user interface touch screen. All three arms can be utilized throughout any of the Urology platform procedures.
MONARCHTM Fluidics Pump Fluidics Pump developed by Thermedx, LLC in partnership with Auris. The system i packaged into a tower enclosure specifically for integration into the MONARCH TM Platform for Urology applications.	
MONARCHTMSingle Controller with buttons and joysticks used to control robotic instrumentation ar adjust system settings and preferences. User holds controller with two hands.	
Percutaneous Sheath Mount	A re-usable mount required to secure and position the Percutaneous Outer Sheath for the MONARCH TM Mini-PCNL procedure.
Compact Field Generator	A re-usable, commercially available electromagnetic field generator that can be positioned near the surgical site. The field generator will be sized appropriately for Guided Percutaneous Access. It requires a mount to be secured to a robotic arm.

# Table 2: MONARCHTM Platform, Urology

Instruments & Access	ories Kits	
Drape Kit	Item	Purpose/Use
MONARCH TM	Controller Drape	Provides a sterile barrier for the MONARCH ™ Controller.
Platform Drape Kit	Cart Drape	Provides a sterile barrier for the MONARCH TM Cart. Sterile adapters are attached to the Cart Drape. Devices are docked to the sterile adapter which are attached to the MONARCH TM Cart.
MONARCH TM Ureter	roscopy	
	MONARCH TM Ureteroscope	A single use Ureteroscope that can be used both robotically and manually. The Ureteroscope will have 2-way, single plane articulation when manually controlled and 4-way, steerable articulation when robotically controlled. The Ureteroscope will also have robotic shaft roll and integrated electromagnetic sensors.
MONARCH™ Ureteroscopy Kit	Ureteroscope Driver	Component that mounts to a robotic arm. Main function is to quickly and safely insert and retract the Ureteroscope into patient and to stabilize the ureteral access sheath. It will be designed to interface with various off the shelf (OTS) ureteral access sheaths.
	Laser Driver	Working channel accessory that mounts to a robotic arm intended to actuate an OTS laser fiber with the MONARCH ™ platform. This accessory will be designed to be compatible with various OTS laser fibers to give users control of insertion/retraction
Printed	copies are considered UNCONTR	OLLED documents after the date printed.
	•	ember 17, 2024.
		ORY OF AURIS HEALTH, INC

PROTOCOL		104-010990-00
First-in-Human Study Protocol – Monarch Urology		С
(Protocol No.: 2021-URO-0001)		47 of 48

			actions. Users will still rely on external laser consoles and foot pedals to activate the laser.	
	Ureteroscope V	alve	Commodity valve and tubing used to connect fluidics to the MONARCH ™ Ureteroscope. One will be included with the kit, and also sold separately in case of sterile contamination.	
Urology Irrigation Cartridge	Urology Irrigati	ion Cartridge	Cartridge and tubing used to connect with the Fluidic Pump. Transfers irrigation from the saline bag to the Ureteroscope or other instruments.	
Stone Retrieval Basket	sket Stone Retrieval Basket		Working channel instrument comprised of a blunt tip basket and handle that mounts to a robotic arm similar to laser driver. User can have full control of the basket to perform insert, retract, open, and close actions. The basket design also allows the user the perform those same actions with the basket non- robotically.	
MONARCH TM Guided I	Percutaneous Ac	cess	· · ·	
Guided Percutaneous Access Kit	Compact Field Generator DrapeCompact Field Generator MountGuided Percutaneous Access Needle		Provides a sterile barrier for the Compact Field Generator.	
			To hold the Compact Field Generator in place and allow for generation of EM field required for Guided Percutaneous Access	
			A needle capable of continuously tracking the 3D location and trajectory of the needle tip using EM sensors to gain precise access into the kidney while minimizing use of fluoroscopy.	
MONARCH ™ Mini-PC	NL			
MONARCH TM Mini- PCNL Kit	MONARCH TM Suction Cathete		Instrument that is a robotically 4-way steerable catheter used for suction and removal of stones during the MONARCH ™ Mini-PCNL procedure.	
	Percutaneous	Percutaneous Outer Sheath	Sheath that interfaces with patient and the percutaneous inner sheath. This sheath provides inflow of fluid from the Fluidics Pump and is stabilized by the Sheath Mount.	
	Sheath	Percutaneous Inner Sheath	Inner sheath that provides a protected channel for the Suction Catheter to enter the patient. The annular space between this inner sheath and the Suction Catheter provides passive outflow of fluid.	
		8Fr Dilator	Standard 8Fr dilator used to dilate the percutaneous tract.	
	Dilation Set	10Fr Catheter	10Fr catheter used to increase the dilation size from 8Fr. Typically used for the placement of a safety guidewire.	
		Percutaneous Sheath Dilator	Sheath dilator used to dilate the tract to the final size for the insertion of the Percutaneous Outer Sheath.	

PROTOCOL		104-010990-00
First-in-Human Study Protocol — Monarch Urology (Protocol No.: 2021-URO-0001)		С
		48 of 48

Suction Set	Suction Cartridge	A suction cartridge needed to connect the suction catheter to standard OR suction equipment. Suction tubing needed to connect the suction
	Alignment Tool	used to orientate and precisely position the robotic arm for docking of the Suction Catheter.
Alignment Set	Alignment Plug	Rigid plug that interfaces with percutaneous sheaths, utilized during an alignment process for positioning the arm used for docking the Suction Catheter. Tool that interfaces with the Alignment Plug and is

This is the Statistical Analysis Plan (SAP) for the final analysis of data collected under Protocol 2021-URO-0001. This SAP describes in detail the statistical methodology and statistical analyses for this protocol.

1.1 Study Objectives

The aim of the study is to collect descriptive performance data on the use of the MONARCHTM Platform, Urology (hereafter referred to as MONARCHTM) for robotic mini-Percutaneous Nephrolithotomy (PCNL) procedures. Data gathered from this study will be used to optimize the robotic platform and inform training and education material for future users.

1.2 Study Design

This is a single-center, prospective, single-arm study to collect descriptive data on the roboticassisted mini-PCNL removal of kidney stones using the MONARCH[™] system.

The study will enroll up to 20 patients. Each enrolled subject will be followed up to 30 days \pm 7 days post procedure.

2 Treatment Assignment

This is a single-arm study where all enrolled subjects will have the MONARCH[™] system utilized for removal of kidney stones via a mini-PCNL procedure.

3 Randomization and Blinding Procedures

As this is a single-arm study, no randomization occurred, and no blinding procedures are required.

4 Interval Windows

Interval windows for the purpose of analysis in this study are not defined outside of those already specified in the protocol for visit scheduling where the collection of data for the primary and safety endpoints occurs.

Table 1 Schedule of Assessments in the protocol specifies the following visit windows:

- Screening/baseline: approximately 30 days prior (allowing up to 60 days prior) to the procedure
- Pre-operative imaging, no longer than 30 days pre-procedure
- Post-operative 30 days follow-up (± 7 days)

Any information entered in the electronic Case Report Forms (eCRFs) at a given visit will correspond to the scheduled visit. There will be no assigning of observations to time points outside of the visit to which they are recorded in the eCRFs.

5 Levels of Significance

No hypotheses are specified for this study and no p-values are being calculated, therefore no level of significance is specified. All estimation of endpoints will be performed using 95% confidence intervals where indicated below.

6 Analysis Sets

The summary of all performance and safety endpoints will be performed on the set of subjects in whom the MONARCHTM system is utilized during the procedure. This will be labeled as the Full Analysis Set (FAS) and will be identified by having a time recorded in the "When was the Ureteroscope introduced (timestamp)?" field on the Procedure: Ureteroscopy and Percutaneous Access eCRF.

7 Sample Size Justification

The study is expected to enroll up to 20 subjects. No formal hypothesis is being tested and therefore the sample size determination is not based on a statistical power calculation, but rather is deemed sufficient for a descriptive summary of safety and primary endpoints in this first-in-human experience with the study device.

8 Analyses to be Conducted

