## Description of the study procedure: Mini-PCNL

This robotically enabled hybrid procedure called the MONARCH™ Mini-PCNL will allow the clinician to obtain retrograde and percutaneous access to patient's kidney under continuous visualization for therapeutic applications (i.e., stone removal). The aim of the study is to evaluate clinical safety and procedural effectiveness of the robotic-assisted diagnostic and therapeutic procedures performed with the MONARCH™ Platform, Urology. The procedure includes the following components.

*Retrograde Access*: The user gains retrograde access to the kidney via conventional cystoscopy techniques and places a ureteral access sheath to maintain access to the kidney.

*Ureteroscopic Surveillance*: The user manually inserts and navigates the ureteroscope to the kidney under direct endoscopic visualization. Once the user confirms access to the kidney, the ureteroscope is docked to the arm IDM. The physician can command insertion/retraction, articulation, and roll of the ureteroscope via the MONARCHTM Controller to survey the kidney and locate the stone.

*Percutaneous Access*: The use of electromagnetic (EM) sensing capabilities provides a rendezvous point with the ureteroscope to guide the advancement of the needle into the kidney under direct visualization and control by the physician. The EM field generator and mount are present on the electromechanical arm by the patient's flank to create the EM field. The user determines which calyx to access and parks the ureteroscope in this calyx. the system creates a virtual target for needle alignment using the ureteroscope's location and orientation and the tower graphical user interface displays trajectory information. Upon gaining access to the kidney, the user will dilate the tract with the MONARCHTM Percutaneous Access Sheath and Dilator set.

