#### • Adverse event

- Any other reason determined by the investigator to be in the best interest of the subject
- Lost to follow-up
- Site termination
- Study termination
- Death

Subjects withdrawn from the Study prior to insertion of the sheath should be converted to conventional ureteroscopy or percutaneous nephrolithotomy. Subjects withdrawn due to an adverse event should be followed until the event has been resolved or is stable, if at all possible.

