#### CONFIDENTIAL, PROPRIETORY OF AURIS HEALTH, INC

First-in-Human Study Protocol – Monarch Urology Rev: C	PROTOCOL	Doc #:	104-010990-00
	First-in-Human Study Protocol – Monarch Urology	Rev:	С
(Protocol No.: 2021-URO-0001) Page: 24 of 48	(Protocol No.: 2021-URO-0001)	Page:	24 of 48

 
Staghorn stone
 
Patient has an electrically or magnetically activated implanted medical device
 
Significant pharmacological anticoagulant therapy or uncorrected
 

bleeding diathesis 13. Tumor in the probable access tract area and potential malignant renal tumor

In addition, subjects will be excluded from participating in this Study if any of the following exclusion criteria occur during the endoscopic procedure.

Intra-Procedure Exclusion Criteria	Any presenting condition discovered intra-procedurally that in the opinion of the investigator would make participating in this study not in the patient's best interest. For example,
	patients no longer considered good candidates for a mini- PCNL procedure for the removal of the kidney stones.

Criteria identified intraoperatively to justify patient exclusion, will be reviewed by the Sponsor, and considered for articulation directly in the protocol for future cases to ensure consistency in exclusion.

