# 7. Assessment of Endpoints

#### **Primary Endpoint**

The primary endpoint is the successful completion of the robotic-assisted kidney stone removal procedures including:

- Gaining safe concomitant (i.e., retrograde and antegrade) access to the upper urinary tract
- Locating and visualizing the kidney stones
- Enabling fragmentation of stones by standard of care method
- Evacuating stone fragments and dust

The above bulleted device endpoints will be assessed regardless of procedural outcome (e.g., evacuation of stone fragments and dust may still be achieved by the device even if the patient is not stone free).

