#### Safety Endpoints

The following will be considered safety endpoints:

- Adverse events through 30-days post-operative, scored on the Clavien-Dindo scale
- Conversion to Conventional Treatment Methods

Adverse events: Adverse events that may have been caused by any component of the procedures including those related to the MONARCHTM Platform, Urology System and/or Components.

Clavien-Dindo scale: Clavien-Dindo system for grading the severity of postoperative complications. See Appendix III.

Conversion to Conventional Treatment Methods: Number of procedures converted to the conventional ureteroscopy or percutaneous nephrolithotomy for any reason.

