# 9.3 Analysis Sets

The summary of all performance and safety endpoints will be performed on the set of subjects in whom the MONARCHTM Platform, Urology is utilized during the surgical procedure.

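### The analysis set starts at ureteroscope introduction, so a case converted earlier, at cystoscopy or access-sheath placement, drops out of the conversion rate

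*SAP*

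**What the plan says.** **Analysis set.** Protocol 9.3: "The summary of all performance and safety endpoints will be performed on the set of subjects in whom the" platform is used during surgery. SAP 6 repeats this, names the set the FAS, and makes it operational: members are "identified by having a time recorded in the 'When was the Ureteroscope introduced (timestamp)?' field" on the ureteroscopy and percutaneous access eCRF.

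**Order of steps.** Protocol 4.2 opens its account of the procedure as follows: "The user gains retrograde access to the kidney via conventional cystoscopy techniques and places a ureteral access sheath to maintain access to the kidney". The ureteroscope is inserted in the next step. Protocol 2.1 describes this first access as conventional and the access sheath as a third-party product.

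**Conversion.** Protocol 4.1 and 7 list conversion as a safety endpoint, defined as: "Number of procedures converted to the conventional ureteroscopy or percutaneous nephrolithotomy for any reason". Protocol 5 adds: "Subjects withdrawn from the Study prior to insertion of the sheath should be converted to conventional ureteroscopy or percutaneous nephrolithotomy". It does not say which sheath is meant. SAP 8.7 places conversion among the additional endpoints, takes it from the Investigator Assessment eCRF, plans counts and percentages, and names no denominator of its own.

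**Intra-procedure exclusion.** Protocol 5.2 says that "subjects will be excluded from participating in this Study if any of the following exclusion criteria occur during the endoscopic procedure".

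**Expectation.** SAP 2 states that the system will be used in all enrolled subjects.

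**The concern.** For the conversion endpoint, entry to the analysis set depends on having passed a stage at which the event can already occur. A procedure that is started, stops at cystoscopy or at the access sheath, and is finished conventionally has no ureteroscope time. If the plan is followed exactly, that case is neither counted as a conversion nor included among the procedures at risk.

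What is at stake is one descriptive rate in a first-in-human report of at most 20 subjects. There is no hypothesis and no decision rule. Even so, a report of no conversions reads differently from a report of one, and the study's stated purpose is to improve the platform and inform training.

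**Working it through.** **Is there a plan figure to reproduce?** No. Neither document gives an expected conversion rate, and both say the sample size is not a statistical calculation.

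**Step 1: can a foreseen conversion precede FAS entry?** Protocol 4.2 gives the order as cystoscopy, ureteral access sheath, ureteroscope, needle access, percutaneous sheath. FAS entry is at the third of these. The Protocol 5 sentence can be read in two ways.

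- If the sheath is the ureteral access sheath, every withdrawal it describes comes before the ureteroscope, and all of these conversions fall outside the FAS.
- If it is the percutaneous sheath, withdrawals at cystoscopy or access-sheath placement fall outside the FAS and later ones fall inside.

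On both readings, some conversions foreseen by the protocol can be left out.

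**Step 2: effect on the rate.** Inputs:

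- Procedures started, n = 20 (planned maximum, SAP 1.2 and 7).
- Conversions before the ureteroscope, k (assumption, 0 to 3; the documents give no figure).
- Later conversions, c (assumption, 0 unless stated).

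Rate in the FAS = c/(n − k). Rate among procedures started = (c + k)/n. The difference, started minus FAS, is

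k(n − k − c) / [n(n − k)],

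which is never negative, so the FAS rate is never the higher one. With c = 0 it reduces to k/n, or 5 percentage points per early conversion when n = 20.

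**Step 3: numbers.** The intervals are exact (Clopper-Pearson) 95%. For x = 0 the upper limit is 1 − 0.025^(1/n); for example, 1 − 0.025^(1/19) = 17.6%. The plan calls for no interval on conversion; these are added for scale.

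| k | c | FAS | Procedures started |
|---|---|---|---|
| 0 | 0 | 0/20 = 0% (0 to 16.8) | 0/20 = 0% (0 to 16.8) |
| 1 | 0 | 0/19 = 0% (0 to 17.6) | 1/20 = 5.0% (0.1 to 24.9) |
| 2 | 0 | 0/18 = 0% (0 to 18.5) | 2/20 = 10.0% (1.2 to 31.7) |
| 3 | 0 | 0/17 = 0% (0 to 19.5) | 3/20 = 15.0% (3.2 to 37.9) |
| 1 | 1 | 1/19 = 5.3% (0.1 to 26.0) | 2/20 = 10.0% (1.2 to 31.7) |

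**Step 4: can the alternative set be identified?** Yes. SAP 8.7 already uses the cystoscope-introduction time from the Pre-Procedure Setup eCRF to define procedure duration.

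**The case against.** The strongest defence is that the protocol's conversion definition describes the event and Protocol 9.3 describes the population, and an event definition does not fix a denominator. SAP 8.7 speaks of conversion to non-robotic treatment, and before the ureteroscope nothing robotic has begun from which to convert. Subjects excluded during the procedure leave the study under Protocol 5.2. SAP 2 expects the FAS and the enrolled subjects to coincide. The SAP follows Protocol 9.3 faithfully, and its past tense in places suggests that conduct was well advanced when it was written.

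Much of this stands. The SAP does apply the protocol, so the tension starts inside the protocol. A device-use set is a defensible choice, and the effect is conditional on an event that no document predicts. It does not remove the point, because Protocol 5 itself uses the word converted for subjects withdrawn before sheath insertion, and the endpoint carries no exemption for them.

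A reader might also infer three stronger things that the documents do not support.

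- *That early adverse events and early stops go unreported.* The protocol's adverse-event endpoint is broad ("Adverse events that may have been caused by any component of the procedures"), Protocol 9.5 commits to summarizing all of them, and SAP 8.8 monitors from consent. SAP 8.2 opens by summarizing disposition in total before limiting the completed and discontinued counts to the FAS. The SAP text between the section 8 heading and 8.2 was also not available here and may bear on this. What remains is a request for clarity.
- *That the FAS is wrong for the primary endpoint.* Protocol 7 says of its components: "The above bulleted device endpoints will be assessed regardless of procedural outcome". A device-use set suits endpoints of that kind.
- *That safety oversight is weakened.* Serious events still go to the sponsor within 24 hours (Protocol 8.2).

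**Conclusion.** The point holds for conversion. Following Protocol 9.3 and SAP 6 exactly can drop a conversion that the protocol defines and foresees, and the effect can only lower the reported rate. With 20 procedures started and no later conversions, each early conversion costs 5 percentage points: 0/19 in place of 1/20, or 0/18 in place of 2/20. That is small beside intervals about 18 to 31 points wide for one or two early conversions. The number of early conversions is assumed throughout; at zero the two sets agree. Severity is minor: this is a cheap improvement in reporting and does not challenge the design or the primary analysis.

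**What to change.** 1. In SAP 6 and 8.7, report conversion on two sets side by side: the FAS, and all subjects with a recorded cystoscope-introduction time. Show intra-procedure exclusions under Protocol 5.2 as their own category, so that a reader can see the rate with and without them.
2. Keep the FAS for the primary endpoint. List each started case outside it with the step that stopped it.
3. Clarify Protocol 9.3 to match, and reconcile the Protocol 5 sentence with Protocol 4.2 so that it is clear which sheath is meant.
4. As a clarification only, and subject to the SAP text before 8.2, state that adverse-event listings and disposition cover all enrolled subjects. Study Exit CRFs are completed for all of them (Protocol 13).

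The cost is SAP wording, a matching protocol clarification, one more denominator, and a possibly less favourable conversion rate. No new field is needed to identify the started set. The sponsor must confirm that the Investigator Assessment eCRF, the source for conversion, is completed for cases stopped early; the documents do not say. Because nothing is tested, adding the second summary late carries no error-rate penalty.
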